#### 4.2 Event Monitoring/Survival Follow-up

	Event Monitoring Phase 				
	q. 3 months until PD	At PD	After PD q. 6 months	Death	New Primary
Event Monitoring	X	X	X	X	At each occurrence

1. If a patient is still alive 3 years after registration, no further follow-up is required.

### 5.0 Grouping Factor

Phase I vs. Phase II

### 6.0 Registration Procedures

#### 6.1 Phase I Registration

**Prior to discussing protocol entry with the patient, call the MCCC Registration Office [REDACTED] for dose level and to insure that a place on the protocol is open to the patient.**

##### 6.11 Registration

To register a patient, fax [REDACTED] a completed eligibility checklist to the Mayo Clinic Cancer Center (MCCC) Registration Office between 8 a.m. and 4:30 p.m. central time Monday through Friday.

##### 6.12 Prior to accepting the registration, the registration/randomization application will verify the following:

- IRB approval at the registering institution
- Patient pre registration eligibility
- Existence of a signed consent form
- Existence of a signed authorization for use and disclosure of protected health information

##### 6.13 Registration tests/procedures (see Section 4.0) must be completed within the guidelines specified on the test schedule.

#### 6.2 Phase II Registration

##### 6.21 Registration

To register a patient, access the Mayo Clinic Cancer Center (MCCC) web page and enter the remote registration/randomization application.

The registration/randomization application is available 24 hours a day, 7 days a week. Back up and/or system support contact information is available on the Web site. If unable to access the Web site, call the MCCC Registration Office at [REDACTED] between the hours of 8 a.m. and 5:00 p.m. Central Time (Monday through Friday).

The instructions for the registration/randomization application are available on the MCCC web page [REDACTED] and detail the process for completing and confirming patient registration. Prior to initiation of protocol treatment, this process must be completed in its entirety and a MCCC

subject ID number must be available as noted in the instructions. It is the responsibility of the individual and institution registering the patient to confirm the process has been successfully completed prior to release of the study agent. Patient registration via the registration/randomization application can be confirmed in any of the following ways:

- Contact the MCCC Registration Office [REDACTED] If the patient was fully registered, the MCCC Registration Office staff can access the information from the centralized database and confirm the registration.
- Refer to “Instructions for Remote Registration” in section “Finding/Displaying Information about A Registered Subject.”

#### 6.22 Verification

Prior to accepting the registration, registration/randomization application will verify the following:

- IRB approval at the registering institution
- Patient eligibility
- Existence of a signed consent form
- Existence of a signed authorization for use and disclosure of protected health information
- Grouping factor

#### 6.3 Both Phase I and Phase II

##### 6.31 Documentation of IRB approval

Documentation of IRB approval must be on file in the Registration Office before an investigator may register any patients.

In addition to submitting initial IRB approval documents, ongoing IRB approval documentation must be on file (no less than annually) at the Registration Office [REDACTED] If the necessary documentation is not submitted in advance of attempting patient registration, the registration will not be accepted and the patient may not be enrolled in the protocol until the situation is resolved.

When the study has been permanently closed to patient enrollment, submission of annual IRB approvals to the Registration Office is no longer necessary.

#### 6.32 Correlative studies

##### 6.321 Mandatory correlative studies

A mandatory correlative component is part of this study. The patient will be automatically registered onto this component (see Section 3.1 and 17.0).

##### 6.322 Optional correlative studies

An optional correlative component is part of this study. At the time of registration, the following will be recorded:

- Patient has/has not given permission to store and use his/her sample(s) for future research of breast cancer at Mayo.
- Patient has/has not given permission to store and use his/her sample(s) for future research to learn, prevent, or treat other health problems.
- Patient has/has not given permission for MCCC to give his/her sample(s) to researchers at other institutions.

## 6.33 Treatment on protocol

Treatment on this protocol must commence at Mayo Clinic under the supervision of a medical oncologist.

## 6.34 Treatment start

Treatment cannot begin prior to registration and must begin  $\leq 14$  days after registration.

## 6.35 Pretreatment

Pretreatment tests/procedures (see [Section 4.0](#)) must be completed within the guidelines specified on the test schedule.

## 6.36 Baseline symptoms

All required baseline symptoms (see [Section 10.6](#)) must be documented and graded.

## 6.37 Study drug availability

Study drug is available on site for this patient.

## 6.38 Retreatment Registration

6.38a To register a patient, fax [REDACTED] a completed retreatment eligibility checklist to the Mayo Clinic Cancer Center (MCCC) Registration Office between 8 a.m. and 4:30 p.m. central time Monday through Friday.

6.38b Treatment cannot begin prior to registration to the retreatment phase and will begin  $\leq 7$  days after registration for the retreatment phase.

## 7.0 Protocol Treatment

### 7.1 Treatment Schedule

#### 7.11 Phase I treatment medication tables

Cycle 1:

Agent	Dose Level	Route	Day
Binimetonib	As assigned by Registration Office	PO BID	1-14

Cycle 2 and all subsequent cycles:

Agent	Dose Level	Route	Day	ReRx
Binimetonib	As assigned by Registration Office	PO BID	1-21	q3w
Pembrolizumab	200 mg	IV	1	q3w

#### 7.12 Phase II treatment medication tables

Cycle 1:

Agent	Dose Level	Route	Day
Binimetonib	As determined by Phase I	PO BID	1-14

Cycle 2 and all subsequent cycles:

Agent	Dose Level	Route	Day	ReRx
Binimetonib	As determined by Phase I	PO BID	1-21	q3w
Pembrolizumab	200 mg	IV	1	q3w

#### 7.13 Treatment Plan

All trial treatments will be administered on an outpatient basis.

In Cycle 1, patients will receive binimetonib for 2 weeks followed by blood draw and optional tumor biopsy to evaluate the effects of binimetonib single agent on immune system and tumors prior to starting pembrolizumab in Cycle 2 and every subsequent cycle.

#### 7.14 Pembrolizumab

Trial treatment should be administered on Day 1 of each cycle after all procedures/assessments have been completed. Trial treatment may be administered up to 3 days before or after the scheduled Day 1 of each cycle due to administrative reasons.

Pembrolizumab at the fixed dose of 200 mg will be administered as a 30 minute IV infusion once every 3 weeks. Every effort should be made to target infusion timing to be as close to 30 minutes as possible. However, given the variability of infusion pumps from site to site, a window of -5 minutes and +10 minutes is permitted (i.e., infusion time is 30 minutes: -5 min/+10 min).

## 7.15 Binimetinib

Binimetinib is an oral medication. Binimetinib will be administered by patients twice daily on a continuous basis.

Given that food-effect clinical studies have shown influence of food on PK of binimetinib is mild and not clinically relevant (see binimetinib Investigator Brochure), binimetinib can be taken with food.

## 7.2 Return to consenting institution

For this protocol, the patient must return to the consenting institution for evaluation at least every 21 days during treatment (Active Monitoring Phase).

## 7.3 Treatment by local medical doctor (LMD)

Treatment by a local medical doctor (LMD) is not allowed.

## 7.4 Phase I – determination of Maximum Tolerated Dose (MTD)

## 7.41 Dose De-Escalation

Dose level	Pembrolizumab**	Binimetinib
-2	200 mg IV q3w	15 mg PO twice daily
-1	200 mg IV q3w	30 mg PO twice daily
0*	200 mg IV q3w	45 mg PO twice daily

**\*starting dose level**

\*\*NOTE: There are no dose modifications for pembrolizumab

If dose level -1 does not meet MTD determination, the study will be stopped and evaluated by the principal investigator and the industry partners to determine an appropriate dose level.

## 7.411 Treatment by a local medical doctor is not allowed.

## 7.412 Three patients will be treated at each dose level and observed for a minimum of 21 days after start of pembrolizumab, to assess toxicities, before new patients are treated. Doses will not be escalated in any individual patient. Decisions on when and how to enroll patients at each dose level are described in Section 16.42.

## 7.413 Investigators are to contact the Study Chair as soon as any dose-limiting toxicity (DLT) occurs.

## 7.42 Definitions of DLT

## 7.421 For this protocol, DLT will be defined as follows for Cycle 2 only:

CTCAE SOC/AE*	Definition (CTCAE Grade)
Blood and lymphatic system disorders	Grade 4
• Febrile neutropenia	
Eye disorders	≥Grade 3
• Blurred vision	
• Flashing lights	
• Floaters	
Eye disorders	Grade 2 lasting >14 consecutive days confirmed by ophthalmic examination Or Grade 3
• Retinopathy	
Eye disorders	Any grade confirmed by ophthalmic examination
• Retinal vascular disorder	

CTCAE SOC/AE*	Definition (CTCAE Grade)
Eye disorders 
 
• Eye disorders, Other specify
 
	Any visual event $\geq$ Grade 3 confirmed by ophthalmic examination
Investigations 
 
• Alanine aminotransferase increased
 
 OR 
 
• Aspartate aminotransferase increased
 
	$\geq$ Grade 3
Investigations 
 
• Blood bilirubin increased
 
	$\geq$ Grade 3
Investigations 
 
• CPK increased
 
	$\geq$ Grade 3 associated with an increase in creatinine $\geq$ 1.5 times patient's baseline (screening) creatinine level
Investigations 
 
• Creatinine increased
 
	$\geq$ Grade 3
Investigations 
 
• Ejection fraction decreased
 
	$\geq$ Grade 3 Or Absolute decrease of LVEF $>$ 10% compared to Baseline and is below the institution's LLN
Investigations 
 
• Electrocardiogram QT corrected interval prolonged
 
	$\geq$ Grade 3 on at least two separate ECGs
Investigations 
 
• Neutrophil count decreased
 
	Grade 4 lasting $>$ 7 consecutive days
Investigations 
 
• Platelet count decreased
 
	Grade 3 with signs of clinically significant bleeding Or Grade 4
Gastrointestinal disorders 
 
• Diarrhea
 
	$\geq$ Grade 3 for $\geq$ 48 hours despite optimal anti-diarrheal therapy Or Grade 4
Gastrointestinal disorders 
 
• Nausea
 
• Vomiting
 
	Grade 3 for $\geq$ 48 hours despite optimal anti-emetic therapy Or Grade 4
General disorders and administration site conditions 
 
• Fatigue
 
	Grade 3 lasting $>$ 14 consecutive days
Skin and subcutaneous tissue disorders 
 
• Rash maculo-papular
 
• Palmar-plantar erythrodysesthesia syndrome
 
• Photosensitivity
 
	Grade 3 lasting $>$ 14 consecutive days despite maximal skin toxicity treatment per local practice Or Grade 4
Vascular disorders 
 
• Hypertension
 
	Grade 3 lasting $>$ 14 consecutive days Or Grade 4
Other events**	Any $\geq$ Grade 3

\*Adverse event at least possibly related to the study medication.

\*\* Lymphocyte count decreased  $\geq$ Grade 3 (unless clinically significant) and Grade 3 alopecia will not be considered a DLT

## 7.5 Retreatment (Second Course Phase)

Patients who stop pembrolizumab and binimetinib with SD or better may be eligible for up to one year of additional pembrolizumab and binimetinib therapy if they progress after

stopping study treatment. This retreatment is termed the Second Course Phase of this study and is only available if the study remains open and the patient meets the following conditions:

EITHER

- Stopped initial treatment with pembrolizumab and binimatinib after attaining an investigator-determined confirmed CR according to RECIST 1.1, and
  - Was treated for at least 24 weeks with pembrolizumab and binimatinib before discontinuing therapy
  - Received at least two cycles with pembrolizumab and binimatinib beyond the date when the initial CR was declared

OR

- Had SD, PR or CR and stopped pembrolizumab and binimatinib treatment after 24 months of study therapy for reasons other than disease progression or intolerance

AND

- Experienced an investigator-determined confirmed radiographic disease progression after stopping their initial treatment with pembrolizumab and binimatinib
- Did not receive any anti-cancer treatment since the last dose of pembrolizumab and binimatinib
- Has a performance status of 0 or 1 on the ECOG Performance Scale
- Demonstrates adequate organ function (as required for initial eligibility in Section 3.0)
- Females of childbearing potential should have a negative serum or urine pregnancy test within 72 hours prior to receiving retreatment with study medication
- Females or males of childbearing potential must be willing to use adequate methods of contraception as outlined in [Section 9.9b](#) or abstain from heterosexual activity for the course of the study through 120 days after the last dose of study medication.
- Does not have a history or current evidence of any condition, therapy, or laboratory abnormality that might interfere with the subject's participation for the full duration of the trial or is not in the best interest of the subject to participate, in the opinion of the treating investigator.

Baseline procedures as outlined in the pretrial screening should be repeated  $\leq 28$  days prior to retreatment.

Patients who restart treatment will be retreated at the same dose and dose interval as when they last received pembrolizumab and binimatinib. Patients may continue treatment for up to one additional year and will follow the original treatment schedule starting at cycle 2.

## 8.0 Dosage Modification Based on Adverse Events

Strictly follow the modifications in this table for the first **two** cycles, until individual treatment tolerance can be ascertained. Thereafter, these modifications should be regarded as guidelines to produce mild-to-moderate, but not debilitating, side effects. If multiple adverse events are seen, administer dose based on greatest reduction required for any single adverse event observed. Reductions or increases apply to treatment given in the preceding cycle and are based on adverse events observed since the prior dose.

→**ALERT:** *ADR reporting may be required for some adverse events (See Section 10.0)←*

\*\* Use the following to describe actions in the Action column:

- Omit = Treatment is not given for this cycle
- Hold/Delay = Treatment can be made up as part of this cycle
- Discontinue = Treatment is totally stopped

**NOTE:** If the patient experiences a significant adverse event requiring a dose reduction at the start of the next cycle, then the dose will remain lowered.

### 8.1 Dose Levels (Based on Adverse Events in Table 8.2)

Dose Level	Binimetinib
0*	45 mg BID
-1	30 mg BID
-2	15 mg BID
-3	Discontinue

\*Dose level 0 refers to the starting dose.

**NOTE:** If binimetinib is discontinued, the patient can continue treatment on single-agent pembrolizumab. The patient will continue to follow the test schedule (Section 4.1)

For binimetinib, if dose reduction goes below -2 dose level, then binimetinib must be discontinued. If binimetinib is started at -2 dose level, then there are no further dose reductions.

NOTE: There are no dose changes for pembrolizumab, only dose schedule modifications.

For patients who do not tolerate the 45 mg BID dosing schedule, dose adjustment to 30 mg BID is permitted in order to allow the patient to continue on study drug. The following guidelines need to be applied and these changes must be recorded on the specific section of the patient record.

A dose reduction below 15 mg BID is not allowed. Dose interruptions of more than 21 days are not allowed.

Missed/skipped doses will not be made up (i.e. the patient should not double their dose if the previous dose was missed). When the adverse event that resulted in a dose reduction improves to and remains stable at Grade 1 or less for a minimum of 21 days, the dose can be re-escalated at the investigators discretion provided there are no other concomitant adverse events.

No dose re-escalation is allowed after dose reduction due to left ventricular dysfunction or prolonged QTcF >500 msec.

Dose reduction/interruption/discontinuation decisions should be based on the CTCAE grade of the adverse event (AE) and the guidelines provided below. In general, doses should not be reduced or interrupted for Grade 1 events, but treatment to control symptoms should be provided as appropriate. All AEs should be followed weekly or as clinically appropriate until stabilization or resolution.

A patient with a Grade 4 AE may resume treatment at the lower dose level if the AE recovers to grade  $\leq 1$  within 21 days of interrupting drug and, if in the opinion of the Investigator and Medical Monitor, the event is not life-threatening, and the patient can be managed and monitored for recurrence of AE. Dose interruptions of more than 21 days are not allowed unless approved by the Investigator, and the Pfizer Inc. (formerly Array Biopharma LLC and Array Biopharma Inc.) Medical Monitor or designee.

Please refer to the table below for dose adjustment recommendations for binimatinib-induced adverse events.

For adverse events that can be attributed to either pembrolizumab or binimatinib, dose adjustment for both agents will be applied. These toxicities include but are not limited to diarrhea and liver function abnormalities.

→ → *Use the NCI Common Terminology Criteria for Adverse Events (CTCAE) current version 4.0\**  
*unless otherwise specified ← ←*

\* Located at [http://ctep.cancer.gov/protocolDevelopment/electronic\\_applications.ctc.htm](http://ctep.cancer.gov/protocolDevelopment/electronic_applications.ctc.htm)

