### Schema

**Phase I Only: Prior to discussing protocol entry with the patient, call the MCCC Registration Office [contact]) for dose level and to insure that a place on the protocol is open to the patient.**

\*Unless adequate tissue is available from biopsy obtained  $\leq$ 90 days prior to registration (see Section 17.0)

\*\*Retreatment (Second Course Phase): Patients who stop pembrolizumab and binimetinib with SD or better may be eligible for up to one year of additional pembrolizumab and binimetinib therapy if they progress after stopping study treatment. This retreatment is termed the Second Course Phase of this study and is only available if the study remains open and the patient meets the requirements as outlined in section 7.5.

Cycle 1 = 14 days

Cycle length for Cycle 2 onward = 21 days

Generic name: pembrolizumab, MK-3475 Brand name(s): Keytruda™ Mayo Abbreviation: MK3475 Availability: Mayo Clinic Pharmacy	Generic name: binimetinib, MEK162 Brand name(s): Mayo Abbreviation: MEK162 Availability: Mayo Clinic Pharmacy
---	--

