## 8.2 Dose Modifications for Binimetinib

CTCAE System/Organ/Class (SOC)	ADVERSE EVENT	Grade	ACTION FOR BINIMETINIB C
Cardiac disorders	Left ventricular systolic dysfunction	Grade 1-2 Asymptomatic absolute decrease of >10% compared to baseline and below institutional LLN	Hold binimetinib and repeat evaluation of LVEF within 2 weeks: 
 
○ If the LVEF recovers (defined as LVEF <math>\geq</math>50% or <math>\geq</math>LLN and absolute decrease <math>\leq</math>10% compared to Baseline) in <math>\leq</math>21 days, reduce 1 dose level after approval of the Principal Investigator. Monitor LVEF 2 weeks after resuming binimetinib, every 4 weeks for 12 weeks and subsequently as per protocol
 
○ If the LVEF does not recover in <math>\leq</math>21 days, permanently discontinue binimetinib. Closely monitor LVEF until resolution or for up to 16 weeks
 
 No dose re-escalation allowed after dose reduction for LVEF
Eye disorders a,b	Retinal detachment	Grade 1	Maintain dose level of binimetinib and increase frequency of ophthalmic monitoring to at least every 14 days until stabilization or resolution
		Grade 2	Maintain dose level of binimetinib and refer the patient to ophthalmologist within 1 week: 
 
○ If resolved to Grade <math>\leq</math>1 in <math>\leq</math>21 days, maintain dose of binimetinib
 
○ If not resolved to Grade <math>\leq</math>1 in <math>\leq</math>21 days, reduce 1 dose level of binimetinib or maintain dose of binimetinib based upon the Investigator's discretion after consultation with the ophthalmologist
 

		Grade 3	Hold binimetinib and refer the patient to ophthalmologist within 1 week: 
 
○ If resolved to Grade <math>\leq</math>1 in <math>\leq</math>21 days, reduce 1 dose level of binimetinib
 
○ If not resolved to Grade <math>\leq</math>1 in <math>\leq</math>21 days, permanently discontinue binimetinib and close follow-up with ophthalmic monitoring until stabilization or resolution
 

		Grade 4	Permanently discontinue binimetinib and immediate follow-up with ophthalmic monitoring until stabilization or resolution
	Retinal vascular disorder (RVO)	Any	Permanently discontinue binimetinib and immediate follow-up with ophthalmic monitoring until stabilization or resolution

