	Eye disorders – Other specify – any non-retinal events	Grade 1-2	Maintain dose level of binimetinib and increase frequency of ophthalmic monitoring to at least every 14 days until stabilization or resolution

CTCAE System/Organ/Class (SOC)	ADVERSE EVENT	Grade	ACTION FOR BINIMETINIB C
Eye disorders a,b	Eye disorders – Other specify – any non-retinal events	Grade 3	
Hold binimetonib and refer patient to ophthalmologist within 1 week:
 
 
○ If resolved to Grade <math>\leq 1</math> in <math>\leq 21</math> days, reduce 1 dose level of binimetonib
 
○ If not resolved to Grade <math>\leq 1</math> in <math>\leq 21</math> days, permanently discontinue binimetonib and close follow-up with ophthalmic monitoring until stabilization or resolution
 

		Grade 4	Permanently discontinue binimetonib and immediate follow-up with ophthalmic monitoring until stabilization or resolution
Gastrointestinal disorders	Diarrhea	Grade 1-2 Uncomplicated	
Consider temporary hold of binimetonib until resolved to Grade <math>\leq 1</math>
 
Resume binimetonib at current dose level

		Grade 1-2 Complicated	
Temporarily hold binimetonib until resolved to Grade <math>\leq 1</math>
 
Resume binimetonib at 1 reduced dose level

		Grade 3	
Temporarily hold binimetonib until resolved to Grade <math>\leq 1</math>
 
Resume binimetonib at 1 reduced dose level

		Grade 4	
Temporarily hold binimetonib until resolved to Grade <math>\leq 1</math>
 
Resume binimetonib at 1 reduced dose level

Investigations	Alanine aminotransferase increased (ALT) OR Aspartate aminotransferase increased (AST)	Grade 1	Maintain dose level of binimetonib
	Alanine aminotransferase increased (ALT) OR Aspartate aminotransferase increased (AST) AND Blood bilirubin increased	Grade 2 For patients with Baseline ALT/AST values <math>\leq</math>ULN: ALT or AST $>3.0$ to $5.0 \times$ ULN and blood bilirubin (total) $\leq 2.0 \times$ ULN	
Hold binimetonib until resolved to Grade <math>\leq 1</math>, then:
 
 
○ If resolved in <math>\leq 14</math> days, maintain dose level of binimetonib
 
○ If not resolved in <math>\leq 14</math> days, reduce 1 dose level of binimetonib
 

CTCAE System/Organ/Class (SOC)	ADVERSE EVENT	Grade	ACTION FOR BINIMETINIB C

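### Section 8.1 lets a patient resume treatment after a Grade 4 adverse event without excepting the binimetinib-related events for which Table 8.2, strict in Cycles 1-2, requires permanent discontinuation

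*Combined protocol and SAP*

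**What the plan says.** Three places in the combined protocol and SAP bear on what happens to binimetinib after a Grade 4 event.

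- **Section 8.0** sets the force of the dose-modification table: "Strictly follow the modifications in this table for the first" two cycles. For later cycles it says: "Thereafter, these modifications should be regarded as guidelines". It also fixes the vocabulary: "Discontinue = Treatment is totally stopped".
- **Section 8.1**, whose heading ties it to the events in Table 8.2, gives a general permission: "A patient with a Grade 4 AE may resume treatment at the lower dose level if the AE recovers to grade" 1 or less within 21 days of interruption. Two further conditions apply. The Investigator and Medical Monitor must consider the event not life-threatening, and the patient must be manageable and monitored for recurrence. No cycle and no attribution is specified. The same section says that dosing decisions rest on the CTCAE grade and the guidelines that follow, and it introduces the table with "Please refer to the table below for dose adjustment recommendations" for events induced by binimetinib.
- **Table 8.2** gives the action by event and grade. For Grade 4 retinal detachment, for example, it reads: "Permanently discontinue binimetinib and immediate follow-up with ophthalmic monitoring until stabilization or resolution".

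Section 9.9f separately directs immediate discontinuation of study drug for Grade 4 rash.

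**The concern.** For most binimetinib-related Grade 4 events, 8.1 and Table 8.2 lead to different actions: conditional resumption at the lower dose level under one, permanent cessation under the other. A reader who goes to 8.1 meets a specific permission with its own safeguards and nothing to say that most Grade 4 rows of the table are outside it. Words such as guidelines and recommendations, placed just before the table, make it easy to treat the table as advice.

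What is at stake is patient safety and consistent conduct. In Cycles 1-2, when every patient is first exposed to binimetinib and then to the combination, a patient who should have stopped binimetinib for good could be given it again. That would be a departure from the table, made in good faith on the words of the protocol.

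**Working it through.** No sample-size or error-rate arithmetic applies. The check is a row count and a comparison of texts.

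**Step 1. Grade 4 rows of Table 8.2 set against 8.1.**

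| Grade 4 row | Table 8.2 action for binimetinib | Against 8.1 |
|---|---|---|
| Retinal detachment | Stop permanently | Differs |
| Other, non-retinal eye events | Stop permanently | Differs |
| Diarrhea | Hold, then resume one level lower | Both allow resumption |
| ALT/AST above 20.0 x ULN | Stop permanently | Differs |
| CPK increased | Asymptomatic: interrupt, reduce one level if resolved within 21 days. Symptomatic: stop permanently | Asymptomatic: both allow resumption. Symptomatic: differs |
| Rash | Stop permanently (also Section 9.9f) | Differs |
| Thromboembolic event | Stop permanently | Differs |
| All other binimetinib-related events | Stop permanently | Differs |

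Count: 6 stop outright + 1 split (CPK) + 1 resume (diarrhea) = 8 rows. The retinal vascular row is graded as any grade and is not counted. Including it would give 6 + 1 = 7 stops in 8 + 1 = 9 rows.

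**Step 2. Which rule has more force, and when.**

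- Cycles 1-2: 8.0 is mandatory and 8.1 is permissive (*may*). Following the table breaches neither text, while resuming under 8.1 in a stop row breaches the table. The table is the better-supported rule.
- Cycle 3 onward: the table is a guideline, so 8.1 and the table no longer collide directly.
- Events unrelated to binimetinib: the table is introduced as covering binimetinib-induced events, and its last row is limited to related ones. Section 8.1 operates there without conflict.

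**Step 3. Length of the strict window.** The Schema gives Cycle 1 as 14 days and states "Cycle length for Cycle 2 onward = 21 days". So 14 + 21 = 35 scheduled days. Sections 13.4 and 13.5 cap treatment at 2 years, or 2 x 365 = 730 days, and 35/730 = 4.8%. This is a share of scheduled time. It says nothing about the share of risk.

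**Step 4. Patients affected.** A patient is affected only if a binimetinib-related Grade 4 event in a stop row (or symptomatic CPK) occurs in Cycles 1-2, recovers to Grade 1 or less within 21 days, and is judged not life-threatening by both parties. The documents give no rate for this combination, so no number can be computed.

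**The case against.** The strongest reply is that the protocol already answers the question. A strict instruction outranks a conditional permission, so the table governs in Cycles 1-2. The heading of 8.1 points to Table 8.2, and 8.1 itself sends discontinuation decisions to the guidance that follows. Section 9.9f settles Grade 4 rash. All of this stands. A reader might infer that nothing in the documents indicates which rule prevails, but that goes too far, because Section 8.0 does so for the first two cycles.

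A reader might also infer an inverted safety rule: Grade 3 ALT/AST at 9 x ULN must stop, because the table stops at above 8.0 x ULN and 8.1 has no Grade 3 route, while Grade 4 at 21 x ULN may be re-challenged. The documents do not support this. It needs the table to bind for Grade 3 but not for Grade 4. In Cycles 1-2 the strict rule stops both, and afterwards both rows are guidelines.

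A harmonised reading has been suggested: since 8.1 speaks of recovery after interrupting the drug, it may apply only where drug is interrupted (diarrhea, asymptomatic CPK, unrelated events) and not where it is discontinued. This is possible, but nothing in 8.1 says so.

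Finally, the 8.1 route is guarded by the Medical Monitor, which makes careless re-challenge less likely. That lowers the risk but does not remove it, because the Medical Monitor would be reading the same unqualified sentence.

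**Conclusion.** The point holds as a missing exception. Section 8.1 permits resumption after any Grade 4 event that meets its conditions. Table 8.2 requires permanent discontinuation in 6 of 8 Grade 4 rows and for symptomatic Grade 4 CPK. Section 8.0 favours the table in Cycles 1-2, but the investigator has to infer that, because 8.1 does not say so and the lead-in to the table softens its status.

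The conclusion rests on two readings: that the table which 8.0 makes strict includes Table 8.2, and that the events concerned are related to binimetinib. It is confined to the 35 scheduled days of Cycles 1-2. The number of affected patients cannot be computed from the documents. Sample size, the ORR analysis and the stopping counts are unaffected. The change is worth making because it concerns patient safety and takes one clause.

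**What to change.** Begin the Grade 4 sentence in 8.1 with: *Except where Table 8.2 requires permanent discontinuation for a binimetinib-related event in Cycles 1-2,* and leave the rest of the sentence as it stands. This keeps the 8.1 route for unrelated Grade 4 events and does not alter the rows where the table itself allows resumption.

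The clinical team should state whether the exception also applies after Cycle 2. Extending it would make those stop rows binding where Section 8.0 now treats them as guidelines. That is a change of clinical policy and should be made deliberately.

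Editorial only: 8.1 states the 21-day limit on interruptions twice, first without and then with the approval exception. Deleting the earlier sentence leaves one consistent rule.

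Cost: one clause, one clinical decision and one deleted sentence, with no change to sample size or analysis.
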